20.2.10 Basal insulin dose (U/day and U/kg/day)

| Population: | FAS and PPS | | |
|-----------------|--|--|--|
| Stratification: | Table: By visit | | |
| | Listing: NA | | |
| Statistics: | The basal insulin dose (U/day and U/kg/day) will be summarised as (n, mean, standard deviation, standard error, median, minimum, maximum) for table. | | |

20.2.11 Change in weight and body mass index at Week 24 from baseline

| FAS and PPS |
|--|
| Table: By visit |
| Listing: By subject |
| The change in weight and body mass index at week 24 from |
| baseline will be summarised as (n, mean, standard deviation, |
| standard error, median, minimum, maximum) and the listing |
| will be presented. |
| |

The change from baseline of weight and body mass index variable will be calculated by using formula mentioned in section 20.1.11.

If the Week 24 result value for weight and body mass index is missing, then nearest previous visit value will be carried forward to week 24 results i.e. LOCF and Efficacy tables will be presented for with and without imputed values separately for each population set.

The change in weight and body mass index from baseline to Week 24 will be analysed using the general linear model.

The change from baseline in weight and body mass index as dependent variable and the baseline value of respective weight and body mass index as covariate.

The estimate, 95% confidence interval and p-value will be summarised for efficacy table.

The percentage change from baseline of weight in kg will also be summarised and efficacy table will be presented.

The regression line for the general linear model without categorical variable is as follows:

 $Y = \alpha + \beta (X)$

Where,

Y= The response change in weight and body mass index.

a =Intercept

 $\beta = slope$

X= Covariate i.e. Baseline weight and body mass index.

The hypothesis is as follows

H0: $\beta = 0$

i.e. There is no statistically significant change in weight and body mass index at Week 24 from baseline depending on the Baseline weight and body mass index.

V/s

H1: β ≠ 0

i.e. There is statistically significant change in weight and body mass index at Week 24 from baseline depending on the Baseline weight and body mass index.

The above hypothesis will be tested based on α (alpha)=0.05, if the p-value \geq 0.05 then we will conclude that there is no statistically significant change in weight and body mass index at Week 4,8,12 and 24 from baseline i.e. Ho is accepted. The sample SAS programme is as follows:

proc mixed data=dataset;

model Y= X / s cl;

estimate "Model with Mean baseline weight and body mass index " int 1 weight and BMI baseline variable mean /CL;

ods output estimates=output dataset; run; quit;

20.2.12 Change in Insulin Treatment Satisfaction Questionnaire (ITSQ) score at Week 24 from Week 4

| Population: | FAS and PPS |
|-------------|-------------|
|-------------|-------------|

Stratification: Table: By visit

Listing: By subject

Statistics: The listing will be presented for ITSQ score and the subject responses to the ITSQ will be reported as transformed overall and domain scores at Weeks 4 and 24 separately.

The domains are categorised as mentioned below:

- Inconvenience of Regimen (IR-5 items)
- Lifestyle Flexibility (LF-3 items)
- Glycemic Control (GC-3 items)
- Hypoglycemic Control (HC-5 items)
- Insulin Delivery Device (DD-6 items)

Transformed domain and overall scores will be calculated based on formula mentioned in section 20.1.12. The transformed domain and overall scores will be summarized by descriptive statistics (n, mean, median, SD, SE, minimum, and maximum) for table.

Missing data imputation will be performed as mentioned in section 8.2 point 4 and Efficacy tables will be presented for with and without imputed values separately for each population set.

The change in transformed domain and overall ITSQ scores score from week 4 to Week 24 will be analysed the general linear model. The change from week 4 in transformed domain and overall ITSQ scores as dependent variable and the week 4 value of transformed domain and overall ITSQ scores as covariate.

The estimate, 95% confidence interval and p-value will be summarised for efficacy table.

The regression line for the general linear model without categorical variable is as follows:

 $Y = \alpha + \beta (X)$

Where,

Y= The response change in transformed domain and overall ITSQ scores.

 $\alpha = Intercept$

β =slope

X= Covariate i.e. week 4 transformed domain and overall ITSQ scores.

The hypothesis is as follows

H0: $\beta = 0$

i.e. There is no statistically significant change in transformed domain and overall ITSQ scores at Week 24 from week 4 depending on the week 4 transformed domain and overall ITSQ scores.

V/s

H1: β≠0

i.e. There is statistically significant change in transformed domain and overall ITSQ scores at Week 24 from week 4

depending on the week 4 transformed domain and overall ITSQ scores.

The above hypothesis will be tested based on α (alpha)=0.05, if the p-value \geq 0.05 then we will conclude that there is no statistically significant change in transformed domain and overall ITSQ scores at week 24 from week 4 i.e. Ho is accepted.

The sample SAS programme is as follows:

proc mixed data=dataset;

model Y= X / s cl;

estimate "Model with Mean transformed domain and overall ITSQ scores" int 1 transformed domain and overall ITSQ scores baseline variable mean /CL;

ods output estimates=output dataset; run; quit;

Page 76 of 85

21. Other assessment

The Physical examination assessment will be presented in data listings and summarised as number and percentage (n and %) for the FAS and PP population set.

Physical examination data will be classified as follows:

- NORMAL
- ABNORMAL

I4L-IN-ABEX(b)

22. Revision history

| Version | Date | Change |
|---------|-----------|-----------------|
| 1 | 02-Dec-19 | Initial Version |

CONFIDENTIAL CS.BS.01.00 TPL-1.0: Statistical Analysis Plan Template

Page 78 of 85

I4L-IN-ABEX(b)

23. Appendix 1: Programming Conventions for Tables, Data Listings and Figures (TLFs)

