## 2. Schedule of Activities

**Table ABEX.1. Schedule of Activities**

Procedure	Screening	Treatment Period							Follow-up	Notes
Visit	1	2	3	4	5	6a	7a	8	9/ET	
Week of Study	-2	0	4	8	12	16	20	24	28	
Allowable Deviation +/- (days)		3	7	7	7	7	7	7		
Informed consent	X									
Subject number assigned	X									
Inclusion and exclusion criteria	X									
Clinical Assessments										
Demography	X									
Full physical examination	X									
Height and weight	X	X						X		Height will be measured only at screening.
Vital signs b	X	X	X	X	X			X	X	SBP, DBP, and PR
Medical history and family history of CV disease	X									
History of substance usage	X									Substances: drugs, alcohol, tobacco, and caffeine
12-lead ECG	X									To be recorded in a resting supine state
Concomitant medication review	X	X	X	X	X	X	X	X	X	
AE/SAE/complaint handling		X	X	X	X	X	X	X	X	
Hypoglycemic events		X	X	X	X	X	X	X	X	
Completion or discontinuation of investigation			X	X	X	X	X	X	X	
FBG c		X	X	X	X					

Procedure	Screening	Treatment Period							Follow-up	Notes
Visit	1	2	3	4	5	6 a	7 a	8	9/ET	
Week of Study	-2	0	4	8	12	16	20	24	28	
Allowable Deviation +/- (days)		3	7	7	7	7	7	7		
7-point SMBG measurement d		X	X	X	X			X		
Laboratory Assessments										
Hematology, clinical chemistry, and urinalysis tests	X				X			X		See Appendix 2 for details. Estimated glomerular filtration rate will be measured only in subjects with a history of severe chronic kidney disease.
Pregnancy test (for WCBP only)	X	X								Serum pregnancy test at Visit 1 and urine pregnancy test at Visit 2 prior to being given the study drug
HIV, hepatitis B and C	X									
HbA1c measurement	X	X			X			X		
Subject-reported outcomes										
ITSQ			X					X		
Ancillary Supplies/Diaries/Study Drug										
Trainings on signs/symptoms of hypo/hyperglycemia and insulin reactions		X	X	X	X	X	X	X		This training is given at baseline and reinforced at every visit of the treatment period
Trainings on injection technique, use of glucometer and 7-point SMBG measurement	X	X	X	X	X			X		This training is given during screening and reinforced at every face-to-face visit of the treatment period

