### Follow-up Visit (Week 28)

All subjects will have a follow-up visit 4 weeks after the last dose of Basaglar. Assessments at this visit will be done as detailed in Section 2. Subjects who withdraw from the study will also have assessments done similar to those at the follow-up visit.

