## 9.5. Subject-Reported Outcomes

Subject-reported outcomes will be measured using the ITSQ at Week 4 and Week 24.

The ITSQ is a validated instrument containing 22 items that assesses treatment satisfaction for subjects taking insulin. Items are measured on a 7-point scale, in which lower scores reflect better outcomes. The items that constitute the 5 domains of satisfaction are categorized as:

- Inconvenience of Regimen (IR – 5 items)
- Lifestyle Flexibility (LF – 3 items)
- Glycemic Control (GC – 3 items)
- Hypoglycemic Control (HC – 5 items), and
- Insulin Delivery Device (DD – 6 items).

The individual raw and transformed domain scores are calculated as follows:

- Step 1: Calculate the raw domain score as the mean of the items in the domain for that subject.
- Step 2: Use the following formula to transform the raw domain scores on a scale from 0 to 100, where higher scores indicate better treatment satisfaction:

$$\text{Transformed domain score} = 100 * [(7 - \text{raw domain score}) / (6)]$$

The individual raw and transformed overall scores are then calculated as follows:

- Step 1: Calculate the raw overall score as the mean of the items for that subject.
- Step 2: Use the following formula to transform the raw overall score on a scale from 0 to 100, where a higher score indicates better treatment satisfaction:

$$\text{Transformed overall score} = 100 * [(7 - \text{raw overall score}) / (6)]$$

If an item score is missing for a subject and  $\leq 20\%$  of the items within the domain (or overall) are missing for that subject, then the mean of the items in the domain (or overall) will be imputed for the missing item score(s). If there are  $>20\%$  missing items, the individual subject domain (or overall) score will be set to missing. Change at Week 24 from Week 4 will be analyzed using the general linear model, with the Week 4 value of the response variable as covariate.

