#### **10.3.3.3. Other Efficacy Parameters**

The following parameters (actual values and change from baseline) will be summarized by descriptive statistics (mean, median, SD, SE, minimum, and maximum) by visit for the FAS population and for the PPS population:

- 7-point SMBG levels (mg/dL and mmol/L)
- body mass index (kg/m^2)
- body weight (kg), and
- basal insulin dose (U/day and U/kg/day).

Additionally, the change from baseline to the Week 24 for 7-point SMBG levels, body mass index, and body weight will be analyzed using the general linear model for the FAS population. The model will evaluate the change from baseline in HbA1c level as the dependent variable, with the baseline value of the variable as covariate, after applying the LOCF method to missing values.

All analyses will be repeated for the PPS population.

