#### **10.3.4. Analyses of Subject-Reported Outcomes**

Subject responses to the ITSQ will be reported as overall and domain scores at Weeks 4 and 24. These scores will be summarized by descriptive statistics (mean, median, SD, SE, minimum, and maximum) by visit for the FAS population. Change at Week 24 from Week 4 will be analyzed using the general linear model, with the Week 4 value of the response variable as covariate, after applying the LOCF method to missing values.

These analyses will be repeated for the PPS population.

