4.2 Schedule of events

The schedule of evaluations and procedures to be performed at specific time points is described in the following table 4.2.

| Procedure | Screening | | | Tre | eatme | ent Pe | eriod | | Follow-up | Notes | |
|--|-----------|---|---|-----|-------|----------------|-----------------------|----|-----------|---|--|
| Visit | 1 | 2 | 3 | 4 | 5 | 6 ^a | 7 ^a | 8 | 9/ET | | |
| Week of Study | -2 | 0 | 4 | 8 | 12 | 16 | 20 | 24 | 28 | | |
| Allowable Deviation +/- (days) | | 3 | 7 | 7 | 7 | 7 | 7 | 7 | | | |
| Informed consent | X | | | | | | | | | | |
| Subject number assigned | Х | | | | | | | | | | |
| Inclusion and exclusion criteria | | | | | | | | | | | |
| Clinical Assessments | | | | | | | | | | | |
| Demography | X | | | | | | | | | | |
| Full physical examination | X | | | | | | | | | | |
| Height and weight | X | X | | | | | | X | | Height will be measured only at screening. | |
| Vital signs ^b | X | X | X | X | Х | | | X | X | SBP, DBP, and PR | |
| Medical history and family history of CV disease | X | | | | | | | | | | |
| History of substance usage | Х | X | X | X | Х | X | X | X | | Substances: drugs, alcohol, tobacco, and caffeine | |
| 12-lead ECG | X | | | | | | | | | To be recorded in a resting supine State | |
| Concomitant medication review | X | X | X | X | Х | X | X | X | X | | |
| AE/SAE/complaint handling | | X | X | X | Х | X | X | X | X | | |
| Hypoglycemic events | | X | X | X | Х | Х | X | X | X | | |
| Completion or discontinuation of investigation | | | × | | Х | X | X | X | X X | | |
| FBG ^c | | X | X | X | Х | | | | | | |
| 7-point SMBG measurement ^d | | X | × | X | X | | | X | | | |
| Laboratory Assessments | | | | | | | | | | | |

Table 4.2

CONFIDENTIAL

Page 14 of 85

CS.BS.01.00 TPL-1.0: Statistical Analysis Plan Template

| Hematology, clinical chemistry, and urinalysis tests | X | | | | X | | | X | | See Appendix 2 of protocol for details. Estimated glomerular filtration rate will be measured only in subjects with a history of severe |
|---|---------------------------|---|---|----|------|----------------|----------------|----|-------------------|--|
| Procedure | Screening | - | | Tr | eatm | ent P | ariad | | Followur | chronic kidney disease. |
| Visit | 1 | 2 | 3 | 4 | 5 | 6 ^a | 7 ^a | 8 | Follow-up 9/ET | Notes |
| Week of Study | -2 | 0 | 4 | | 12 | 16 | 20 | 24 | 28 | |
| Allowable Deviation +/- (days) | | 3 | 7 | 7 | 7 | 7 | 7 | 7 | 20 | |

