7.2 Baseline

Unless stated otherwise, baseline is defined as the last non-missing observation made prior to the first administration of IMP. if multiple values pre-treatment exists then the value closes to first treatment administration will be considered as baseline.

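### For weight, BMI and ITSQ, LOCF can only impute a Week 24 change of exactly zero, and the plan does not say whether the imputed or the unimputed analysis is the main result

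*SAP*

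**What the plan says.** **Measurement times.** The schedule row in SAP 4.2 reads "Height and weight | X | X | | | | | | X", which is Visits 1, 2 and 8 (Weeks -2, 0 and 24). Protocol Table ABEX.1 has the same ticks and notes: "Height will be measured only at screening". BMI change therefore follows weight change. For the questionnaire, protocol 9.5 says: "Subject-reported outcomes will be measured using the ITSQ at Week 4 and Week 24". On early termination, protocol 5.1.1 says: "Subjects who withdraw from the study will also have assessments done similar to those at the follow-up visit". The 9/ET column contains neither weight nor ITSQ.

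**Reference values.** Under SAP 7.2, "baseline is defined as the last non-missing observation made prior to the first administration of IMP". For weight this is normally Visit 2. ITSQ change is taken from Week 4.

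**Imputation.** Protocol 10.3.3.3 fits the general linear model for BMI and weight "after applying the LOCF method to missing values". Protocol 10.3.4 fits the ITSQ model "with the Week 4 value of the response variable as covariate, after applying the LOCF method to missing values". SAP 8.2 lists LOCF for all three measures, and SAP 20.2.11 gives the weight and BMI rule: "nearest previous visit value will be carried forward to week 24 results".

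**Other versions.** SAP 20.2.11 and 20.2.12 ask for efficacy tables both with and without imputation, for the FAS and the per-protocol set (PPS). They do not say which is the main one. The protocol synopsis (other continuous secondary measures) and protocol 9.5 (ITSQ) describe the same models without mentioning LOCF.

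**The concern.** LOCF is normally defended as using the last follow-up information available. Here there is none to use. HbA1c, 7-point SMBG, laboratory tests and vital signs all have a scheduled post-baseline value before Week 24. Weight, BMI and ITSQ have no scheduled value between the reference and Week 24. For them the rule amounts to assuming no change in anyone without a Week 24 value.

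Two things follow. The estimated mean change is pulled towards zero in proportion to drop-out. The added zeros also count as observations, so the standard error is computed on subjects who contributed no data on change. Weight change on insulin is a safety-relevant result in a study whose purpose is safety, and the only model that protocol 10.3.3.3 and 10.3.4 specify is the one with this built-in pull.

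**Working it through.** **The plan's own figures.** Completers and drop-out: 200 / (1 - 0.20) = 250 enrolled. Screening: 250 / (1 - 0.15) = 294.1, stated as about 295. Both reproduce. At 20% drop-out, 50 of 250 FAS subjects lack Week 24 data.

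**Step 1: the imputed change.**
- Weight: the nearest previous scheduled value is Visit 2, which is the baseline. If Visit 2 is missing, screening becomes both the baseline and the carried value. The change is 0 either way.
- BMI: height is fixed, so the change is 0.
- ITSQ: the only earlier value is Week 4, which is the reference. The change is 0 for anyone with a Week 4 score. Subjects who leave before Week 4 have nothing to carry and drop out of the model.

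**Step 2: the mean.** The SAP's model, estimated at the mean baseline, returns the sample mean of the changes. With drop-out share d, LOCF mean = (1 - d) × completers' mean.
- Weight and BMI at 20%: 200/250 = 0.80. At 10% and 30% drop-out the factor is 0.90 and 0.70.
- ITSQ, if a share f of the 50 drop-outs leaves before Week 4 (assumed, as the documents give no timing): factor = 200 / (250 - 50f). For f = 0, 10%, 25% and 50% this is 0.80, 0.82, 0.84 and 0.89.

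**Step 3: the interval and its coverage (weight and BMI).** The documents give no expected change or SD for these measures, so I work in r = true mean change / SD over an assumed range. I also assume that drop-outs would have had the same distribution of change as completers. In SD units:
- unimputed SE = 1/√200 = 0.0707, half-width 1.96 × 0.0707 = 0.139
- LOCF SE = √{[(1 - d) + d(1 - d)r²] / 250}, which at d = 0.20 is √[(0.8 + 0.16r²)/250]
- bias = -d × r = -0.2r
- coverage = Φ(1.96 - 0.2r/SE) - Φ(-1.96 - 0.2r/SE)

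| r | Unimputed half-width | LOCF half-width | Ratio | LOCF coverage of true change |
|---|---|---|---|---|
| 0.3 | 0.139 | 0.112 | 0.81 | 82% |
| 0.5 | 0.139 | 0.114 | 0.82 | 59% |
| 1.0 | 0.139 | 0.121 | 0.88 | 10% |
| 2.0 | 0.139 | 0.149 | 1.07 | about 0% |

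For r from 0.3 to 1.0 the LOCF interval is 12 to 19% narrower than the unimputed one. It is also narrower than complete follow-up of all 250 would give (1.96/√250 = 0.124). The ratio reaches 1 when (1 - d)²(1 + d r²) = 1. At d = 0.20 that gives r² = (1/0.64 - 1)/0.20 = 2.8125, so r = 1.68. Above that the LOCF interval is wider.

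Coverage at r = 0.3, 0.5 and 1.0 is 92%, 87% and 64% at 10% drop-out, and 61%, 22% and about 0% at 30%.

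**Step 4: simulation of the planned model.** I regressed change on baseline with 50 of 250 missing completely at random (5,000 runs, assumed slope -0.20). For true changes of 0.3, 0.5 and 1.0 SD, LOCF estimated 0.24, 0.40 and 0.80, with coverage of 82%, 58% and 8%. The unimputed model covered in 94 to 95% of runs. The baseline slope shrank from -0.20 to -0.16 under LOCF.

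**In kilograms (illustration, assumed gain 2.0 kg and SD 3.0 kg).** LOCF mean = 0.8 × 2.0 = 1.6 kg. Variance = 0.8 × (9 + 4) - 1.6² = 7.84, so SE = 2.8/√250 = 0.18, against 3/√200 = 0.21 unimputed. The LOCF 95% interval centres on about 1.25 to 1.95 kg, and coverage of 2.0 kg is about 38%.

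**The case against.** The best defence is that the plan already contains the remedy. SAP 20.2.11 and 20.2.12 require unimputed tables beside the LOCF tables, and the PPS repeat excludes anyone who discontinued before Week 24, so it has almost none of these zeros. A reader might infer from the LOCF rule that weight gain will be hidden. The documents do not support that. The unimputed estimate will be reported, the synopsis and protocol 9.5 give the models without LOCF, and even the LOCF estimate in the kilogram illustration stays well away from zero. The effect is attenuation.

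Three other stronger readings also fail. The interval is not always too narrow: that depends on a standardised change below about 1.68 at 20% drop-out. Not every drop-out receives a zero on the ITSQ, because early leavers have no Week 4 score. The shortfall is not certain bias: if drop-outs gained less than completers, it is smaller, and zero would be right for subjects who truly did not change. The protocol allows withdrawal for persistent hypoglycemia and treats significant noncompliance as withdrawal, so non-random exit is plausible.

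It is also fair to say that the unimputed analysis makes its own assumption about drop-outs and recovers no missing data.

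What survives is that the two FAS estimates will differ by a fixed, predictable factor, the SAP does not rank them, and the protocol's detailed sections name the attenuated one. No document argues that no change is the expected course for drop-outs.

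**Conclusion.** The concern holds as a matter of analysis choice and ranking. From the scheduled data, LOCF gives a change of exactly zero to every FAS subject without a Week 24 weight or BMI, and to every subject with a Week 4 but no Week 24 ITSQ score. The mean factor of 0.80 for weight and BMI at 20% missing is arithmetic and needs no assumption about effect size. The ITSQ range of 0.80 to 0.89 rests on an assumed timing of drop-out. The interval and coverage figures rest on an assumed range of standardised change and on drop-outs resembling completers. These are secondary endpoints. The primary hypoglycemia incidence is unaffected, and the PPS results nearly so. The point deserves correction before analysis but does not threaten the study's main conclusion.

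**What to change.** In protocol 10.3.3.3 and 10.3.4 and SAP 8.2, 20.2.11 and 20.2.12:

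- Name the unimputed, baseline-adjusted general linear model as the main analysis of change in weight, BMI and ITSQ (for ITSQ, adjusted for the Week 4 score).
- State the number of subjects contributing and the missing-at-random assumption beside each estimate.
- Drop LOCF for these three measures, or keep it as a supportive analysis labelled as a scenario in which subjects without Week 24 data did not change.
- Keep the wording consistent with the synopsis and protocol 9.5, which already give the models without LOCF.

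The cost is wording, since the unimputed tables are already planned. The main-analysis n falls to subjects with Week 24 data, about 200 of 250 at the planned drop-out, with a half-width for weight and BMI of about 0.139 SD. No extra visits or subjects are needed. The change does not recover the missing values, so the text should not suggest that it does.

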23.1 Paper Size, Orientation and Margins

The margin, page size and line size specifications as stipulated in Table 20.1 will be used for the presentation of all TLFs.

| | Landscape |
|----------------------------------|-----------|
| Margins (Inches): | |
| Тор | 1 |
| Bottom | 1 |
| Left | 1 |
| Right | 1 |
| SAS [®] specifications: | |
| PAGESIZE | 46 |
| LINE SIZE | 134 |

Table 23.1: Output margin, page size and line size specifications

